#### **5.1.2.1 Prior therapies date imputation**

Same imputation rules as for concomitant medication date imputation.

#### **5.1.2.2 Other imputations**

Not applicable.

### **5.2 AEs coding/grading**

Coding of AE will be done per MedDRA dictionary.

#### **5.2.1 Search criteria for other safety topics:MACE**

The search criteria of MACE will be based on the eCRS and the following outcome data (fatal/non-fatal).

Major cardiovascular events (MACE)

Cardiac death

- Fatal SAEs in Cardiac disorders SOC

- Fatal SAEs in General disorder SOC: PTs 'Death', 'Sudden cardiac death', 'Cardiac death', 'Apparent death'

**Cardiac arrest**

- PT 'Cardiac arrest'

**Non-fatal MI**

- Myocardial infarction (SMQ, broad and narrow), nonfatal events only

**Stroke**

- Central Nervous System hemorrhages and cerebrovascular accidents (HLT), non-fatal events

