### **2.8.1.1 Adverse events of special interest / grouping of AEs**

In order to support the additional assessment of adverse events, adverse events of special interest and other safety topics will be summarized by treatment group, including the number (and proportion) of participants. In addition, the adverse events of special interest will also be summarized by seriousness and severity, and other safety topics will be summarized by seriousness. Adverse events of special interest and other safety topics used in this analysis are specified as follows. The search criteria including subcategoires will be defined in detail in an external file according to the latest version of eCRS at the DBL. This includes MedDRA version and Novartis MedDRA Query (NMQ) dictionary date. However, for major cardiovascular events (MACE), the outcome data (fatal/non-fatal) will also be used, the details is provided in [Appendix 5.2](#).

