#### Other safety topics

- Renal events
- Hypersensitivity reactions
- Neurological events
- Neurocognitive disorders
- Ophthalmological events
- Major cardiovascular events (MACE)

The eCRS safety definitions used to identify AEs of special interest and other safety topics will be provided as a listing.

The number and percentage of participants who had injection site reactions (sign and symptom) will be summarized and listed.

Listing of participants with adverse event of special interest and other safety topics will be provided.

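### The MACE criteria printed in SAP 5.2.1 count a stroke the participant survives but give no route for a fatal one

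*SAP*

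**What the plan says.** SAP 2.8.1.1 lists MACE among the other safety topics, to be summarized by treatment group and by seriousness. Search criteria for these topics are generally left to an external eCRS file, but MACE is singled out: "for major cardiovascular events (MACE), the outcome data (fatal/non-fatal) will also be used", with the detail placed in Appendix 5.2.

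Appendix 5.2.1 then prints these criteria:

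- Cardiac death, first part: "Fatal SAEs in Cardiac disorders SOC".
- Cardiac death, second part: fatal SAEs in the general disorders SOC under four named preferred terms (death, sudden cardiac death, cardiac death, apparent death).
- Cardiac arrest: a single preferred term, with no restriction on outcome.
- Non-fatal MI: "Myocardial infarction (SMQ, broad and narrow), nonfatal events only".
- Stroke: "Central Nervous System hemorrhages and cerebrovascular accidents (HLT), non-fatal events".

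Protocol 8.4.4.2 gives examples of CV events to be collected as AE data. It sets non-fatal stroke beside CV death, which is broader than the SAP's cardiac death.

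**The concern.** Limiting a component to non-fatal events works when another component picks up the fatal ones. For MI that holds, because a fatal MI in the Cardiac disorders SOC returns as cardiac death. The stroke row carries the same limit, but the death row is confined to cardiac and unspecified deaths, so a fatal stroke has no way back in. The heading of that row is simply Stroke, so a reader of the table would not expect the fatal cases to be missing.

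The enrolled population includes people with prior non-cardiogenic cerebral infarction, CAD or PAD, so stroke is a relevant event. A MACE row that counts survived strokes and omits fatal ones leaves out the worse outcome. At stake is the accuracy of one descriptive safety summary. No hypothesis test or estimand depends on it.

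**Working it through.** The plan states no figure to reproduce. The check is whether a given event meets any printed criterion in SAP 5.2.1. It takes the stroke HLT to lie outside the Cardiac disorders SOC, as its name indicates.

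| Criterion | Fatal stroke, no other event | Same stroke, survived | Fatal MI in the Cardiac disorders SOC |
|---|---|---|---|
| Fatal SAE, Cardiac disorders SOC | No: different SOC | No | **Yes** |
| Fatal SAE, four general death terms | No: not one of the terms | No | No |
| Cardiac arrest term | No | No | No |
| MI, non-fatal only | No | No | No: fatal |
| Stroke HLT, non-fatal only | No: fatal | **Yes** | No |
| Counted as MACE | **No** | **Yes** | **Yes** |

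A participant who also has a cardiac arrest term, a fatal SAE coded to one of the four death terms, or an earlier non-fatal MI or stroke is already counted. The gap concerns only participants whose sole qualifying event is a fatal stroke.

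**Size.** Understatement of an arm's MACE percentage = 100 × k/n. Here k is the number of participants omitted in that arm, and n is the planned arm size (SAP 1.1 and section 3: 100, 100, 54 and 54), taken as the size of the safety set. The documents give no fatal-stroke rate, so k is an assumption shown over a range.

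| k (assumed) | n = 100 (200 mg or 300 mg) | n = 54 (100 mg or placebo) |
|---|---|---|
| 0 | 0 | 0 |
| 1 | 1/100 = 1.0 point | 1/54 = 1.85, about 1.9 points |
| 2 | 2/100 = 2.0 points | 2/54 = 3.70, about 3.7 points |

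Protocol 12.4.3 and SAP 2.5.3 both expect few deaths of any cause, so k = 0 is plausible.

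**The case against.** The strongest objection is that the printed list is not the only source. SAP 5.2.1 states: "The search criteria of MACE will be based on the eCRS and the following outcome data (fatal/non-fatal"). The eCRS is not among the documents and might contain a fatal cerebrovascular term. This stands as a limit on what can be claimed: the finding is about the printed criteria, not about the table as it will be programmed. It does not remove the problem, because SAP 2.8.1.1 sends the fatal/non-fatal rule for MACE to the appendix, and the appendix restricts stroke to non-fatal events. If the eCRS does capture fatal stroke, the two sources conflict and need reconciling.

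Second, no document requires MACE to include fatal stroke, and the protocol's list is illustrative rather than a MACE definition. That is fair, and no breach of the protocol is claimed. The case rests on the SAP's own asymmetry between MI and stroke.

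Third, a fatal stroke would still appear in the death and SAE outputs (SAP 2.8.1 and 2.8.2), and the definitions will be disclosed: "The eCRS safety definitions used to identify AEs of special interest and other safety topics will be provided as a listing". This is correct and limits the consequence to the grouping in one row. A reader of the MACE table should still not have to rebuild it from the death listings. A footnote pointing to those outputs would disclose the gap but leave the count unchanged.

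Fourth, the range for k has no empirical basis. That also stands: the percentages show what each omission is worth, not how likely one is.

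**Conclusion.** The concern holds on the printed text. A participant whose only qualifying event is a fatal stroke meets none of the criteria in SAP 5.2.1, although a survived stroke and a fatal MI are both counted. Each omission is worth 1.0 point in an arm of 100 and 1.9 points in an arm of 54; the number of omissions is unknown and may be zero. The conclusion assumes that the stroke HLT lies outside the Cardiac disorders SOC and that the eCRS does not override the printed outcome filter. The effect is limited to a descriptive safety summary. The definition should be corrected, but the point does not threaten the trial's conclusions on efficacy.

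**What to change.** Amend Appendix 5.2.1 in one of two ways:

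- (a) Remove the non-fatal restriction from the stroke row.
- (b) Add fatal events of the stroke HLT to the death row and rename that row CV death. This keeps stroke as a non-fatal component and matches the pairing in Protocol 8.4.4.2.

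Under either option, count each participant once in the MACE total and bring the eCRS file into line with the chosen wording.

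The edit is small and uses outcome data that the SAP already applies to MACE. The main cost is timing. The Document History dates the latest SAP versions after the primary analysis, when Protocol 6.4 allows sponsor members other than the blinded monitors to be unblinded. The change should therefore be recorded as made after that point, and the end-of-study MACE output reconciled with the Day 180 output. The MACE count can only stay the same or rise.

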### 5.3      **Laboratory parameters derivations**

Notable laboratory values are defined as follows.

**Table 5.3-1 Clinically notable laboratory abnormalities for selected tests**

Parameters	Criteria
Hematology	
Hemoglobin	≤ 10 g/dL
Hematocrit	≤ 0.8 × LLN
WBC (total)	≤ 2.8 ×10  / μL, ≥ 16 ×10  / μL
Platelet count	≤ 75 ×10  / μL, ≥ 700 ×10  / μL
HbA1c	≥ 6.5% and ≥0.5% change from baseline
Clinically chemistry	
Creatinine	> 2 mg/dL
CK	> 1 and ≤ 3 × ULN
CK	> 3 and ≤ 5 × ULN
CK	> 5 and ≤ 10 × ULN
CK	> 10 × ULN
ALT	> 1 and ≤ 3 × ULN
ALT	> 3 and ≤ 5 × ULN
ALT	> 5 and ≤ 10 × ULN
ALT	> 10 × ULN
AST	> 1 and ≤ 3 × ULN
AST	> 3 and ≤ 5 × ULN
AST	> 5 and ≤ 10 × ULN
AST	> 10 × ULN

Parameters	Criteria
Total bilirubin	$> 2 \times \text{ULN}$
ALP	$> 2 \times \text{ULN}$

**Table 5.3-2 Notable liver function test values**

Criterion
ALT > 3 x the upper limit of normal range (ULN)
ALT > 5 x ULN
ALT > 8 x ULN
ALT > 10 x ULN
ALT > 20 x ULN
AST > 3 x ULN
AST > 5 x ULN
AST > 8 x ULN
AST > 10 x ULN
AST > 20 x ULN
ALT or AST > 3 x ULN
ALT or AST > 5 x ULN
ALT or AST > 8 x ULN
ALT or AST > 10 x ULN
ALT or AST > 20 x ULN
Total bilirubin > 1 x ULN
Total bilirubin > 1.5 x ULN
Total bilirubin > 2 x ULN
Total bilirubin > 3 x ULN
TBL >2xULN & DBL >ULN
TBL >2xULN & DBL >1.5xULN
TBL >2xULN & DBL >2xULN
ALP > 1.5 x ULN
ALP > 2 x ULN
ALP > 3 x ULN
ALP > 5 x ULN
ALT or AST > 3 x ULN and total bilirubin > 1.5 x ULN
ALT or AST > 3 x ULN and total bilirubin > 2 x ULN
ALT or AST > 5 x ULN and total bilirubin > 2 x ULN
ALT or AST > 8 x ULN and total bilirubin > 2 x ULN
ALT or AST > 10 x ULN and total bilirubin > 2 x ULN
ALT or AST > 20 x ULN and total bilirubin > 2 x ULN
ALP > 3 x ULN and total bilirubin > 2 x ULN
ALP > 5 x ULN and total bilirubin > 2 x ULN
ALT or AST > 3 x ULN and Total Bilirubin > 2 x ULN and ALP < 2 x ULN (Hy's law)

ALT = alanine aminotransferase, AST = aspartate aminotransferase, ALP = alkaline phosphatase,  
DBL = Direct bilirubin

## 5.4 Statistical models

A horizontal bar chart consisting of 15 bars of varying lengths. The bars are black on a white background. The first bar is the longest, followed by a short bar, then a medium bar, then a long bar, then a short bar, then a long bar, then a medium bar, then a long bar, then a short bar, then a long bar, then a medium bar, then a long bar, then a short bar, then a long bar, and finally a very long bar. The bars are separated by small gaps.

A series of black horizontal bars of varying lengths, with the first bar being the longest and subsequent bars getting progressively shorter. The bars are positioned vertically, creating a stepped or layered effect. The first bar is approximately 80% of the page height, the second is about 70%, the third is about 60%, the fourth is about 50%, the fifth is about 40%, the sixth is about 30%, and the seventh is about 20%.

### 5.4.3 Key secondary analysis

Same analysis will be applied on the key secondary endpoints.

## 5.5 Responder definition

The following table explains Japanese lipid modification targets according to participant's background risk categories as per the JAS 2017 guideline.

Participant's background risk categories as per the JAS 2017 guideline	LDL-C targets
Participant with history of CAD with additional risk factors such as HeFH, ACS or diabetes complicated by other risk factors	Serum LDL-C <70 mg/dL
Participant with history of CAD without additional risk factors or HeFH participant without CAD history	Serum LDL-C <100 mg/dL
Participant categorized in 'high risk'	Serum LDL-C <120 mg/dL

The following table explains Japanese lipid modification targets according to participant's background risk categories as per the JAS 2022 guideline.

Participant's background risk categories as per the JAS 2022 guideline	Additional background categories as per the JAS 2022 guideline	LDL-C targets
Participants with a medical history (MH) of cerebral Infarction (Occurrence=Yes) excluding lacunar infarction	MH of CAD, FH, DM [Programming note] CAD: Coronary artery disease (Occurrence=Yes) FH: Heterozygous familial hypercholesterolemia (Ongoing=Yes) DM Diabetes mellitus (Occurrence=Yes)	Serum LDL-C <70 mg/dL
	Except for the above,	Serum LDL-C <100 mg/dL
Participants other than the above and were classified as target value Serum LDL-C $\geq$ 100 mg/dL at baseline and Participants with MH of CAD	MH of DM	Serum LDL-C <70 mg/dL
	Except for the above,	Serum LDL-C <100 mg/dL
Participants other than the above and were classified as target value Serum LDL-C $\geq$ 70 mg/dL at baseline		Serum LDL-C <70 mg/dL
HeFH (MH of HeFH) participants other than the above	No MH of cerebral Infarction excluding lacunar infarction or No MH of CAD	Serum LDL-C <100 mg/dL

DM (MH of DM) participants other than the above	
Smoking (Current) [Programming note] current smoking status category=Current
 
OR
 
Retinopathy (ongoing) [Programming note] PT= Diabetic retinopathy & Ongoing=Yes
 
OR
 
Nephropathy (ongoing): [Programming note] PT=Diabetic nephropathy & Ongoing=Yes PT=Nephrotic syndrome & Ongoing=Yes
 
OR
 
Neuropathy (ongoing): [Programming note] PT=Diabetic neuropathy &Ongoing=Yes PT=peripheral neuropathy & Ongoing=Yes
 
OR
 
PAD (ongoing): [Programming note] PT=Peripheral arterial occlusive disease & Ongoing=Yes PT=peripheral artery occlusion & Ongoing=Yes
	Serum LDL-C <100 mg/dL
Participants other than the above		Serum LDL-C <120 mg/dL

The following calculations are defined to determine whether a subject has >80% of baseline at Day 180. [REDACTED]

1. Threshold=80% \* (LDL-C at Baseline - LDL-C at Day180) + LDL-C at Day180.
2. If the subject's LDL-C value is greater than the threshold specified above, or the subject's LDL-C value is greater than or equal to the LDL-C at Baseline, the subject is considered to have >80% of baseline.

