17-May-2022	Prior to DB lock		

Added list for the ADA evaluations.

Updated according to the eCRS

Added the analysis window for each scheduled visit.

Added responder definition as per the JAS 2017 guideline and 80% of the baseline value at Day 180

Removed the analysis window,

Updated the DM subgroup.

Updated the LDL-C group and added Screening LDL-C.

Removed on-treatment for individual responsiveness

Added 5% cut-off for the TEAE table.

Updated adverse events of special interest and added other safety topics

Updated the HbA1c category

Added the average in the listing.

Updated CM data imputation.

Updated AE of special interest.

	

2.8.4 Diabetes assessment

2.10 Immunogenicity

5.2.1 Search criteria for AESI

5.1.1 Analysis Windows

5.5. Responder definition

2.1.1 General definitions, 5.1 Imputation rules

2.2.1 Subgroup of interest

2.3.1 Demographics and other baseline characteristics

2.7.1 Secondary endpoints

[REDACTED]

2.8.1 Adverse events

2.8.1.1 Adverse events of special interest/grouping of AEs

2.8.3 Laboratory data

2.8.6 Vital signs

5.1.2 Concomitant medication date imputation.

5.2.1 Search criteria for AE of special interest

Date	Time point	Reason for update	Outcome for update	Section and title impacted (Current)
17-Oct-2022	Prior to final DB Lock (after primary analysis)	JAS guideline was updated (after primary analysis)	Added analyses according to JAS-2022 guideline.	

• Table 1.2

• 2.7.1 Secondary endpoints

  

• 4 Change to protocol specified analyses

• 5.5 Responder definition

18-Oct-2022	Prior to final DB Lock (after primary analysis)	No need for EudraCT	Deleted analyses for EudraCT only	

• 2.8.1 Adverse events (AEs)

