## **2.7 Analysis of other secondary efficacy objective(s)**

### **2.7.1 Secondary endpoints**

The other secondary efficacy objectives of this study are to evaluate the effect of inclisiran on the following:

- Percentage change in PCSK9 levels from baseline to Days 14, 30, 60, 90, 104, 120, and 150
- Percentage change in LDL-C from baseline to Days 14, 30, 60, 90, 104, 120, and 150
- Proportion of participants in each group with LDL-C greater than 80% of the baseline value at Day 180 ([Appendix 5.5](#))
- Percentage change in other lipids, lipoproteins, apolipoproteins from baseline to Days 14, 30, 60, 90, 104, 120, 150, and 180
- Proportion of participants in each group with greater or equal to 50% LDL-C reduction from baseline at Days 14, 30, 60, 90, 104, 120, 150, and 180
- Individual responsiveness defined as the number of participants reaching LDL-C levels of <25 mg/dL, <50 mg/dL, <70 mg/dL, and <100 mg/dL at Days 14, 30, 60, 90, 104, 120, 150, and 180
- Proportion of participants in each group who attain Japanese lipid modification targets specified by JAS-2017 and JAS-2022 guidelines ([Appendix 5.5](#)) for their level of cardiovascular risk at Day 180

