### **2.7.2 Statistical hypothesis, model, and method of analysis**

- For other secondary endpoints, only the descriptive statistics by treatment group will be presented. The two-sided 95% confidence interval for the proportion will be provided using the exact method of Clopper and Pearson.

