### 3 Sample size calculation

Approximately 308 participants will be randomized by the IRT system: 100 participants for inclisiran sodium dose groups 200 mg and 300 mg; plus 54 participants in the placebo group and inclisiran sodium dose group 100 mg. Randomization will be stratified by current use of statins or other lipid-modifying therapies, LDL-C category at screening, [REDACTED].

The sample size assumption was based on the observed results from a previously completed Phase II Dose Finding Study (ORION-1). The difference in mean percentage change from baseline between the active dose groups and the placebo group for LDL-C at Day 180 is expected to be >30% with a standard deviation of approximately 20%.

The sample size of 308 will provide more than 90% power to detect a 30% reduction of LDL-C levels in at least one inclisiran sodium dose group compared to the placebo. Dunnett's test is used in order to control the family-wise type I error rate at a significance level of alpha=0.025 (one-sided test). [REDACTED].

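### SAP 5.5: the printed rule for LDL-C above 80% of baseline at Day 180 does not give that cut-off; on Day 180 values it counts only LDL-C at or above baseline

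*SAP*

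**What the plan says.** Protocol Table 2-1 and section 12.5.1, and SAP Table 1-2 and section 2.7.1, word the endpoint identically: "Proportion of participants in each group with LDL-C greater than 80% of the baseline value at Day 180". SAP 2.7.1 attaches a reference to Appendix 5.5.

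The visible lead-in in Appendix 5.5 reads "The following calculations are defined to determine whether a subject has >80% of baseline at Day 180". A redaction follows, then two steps:

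- **Step 1** defines a threshold as 80% × ("LDL-C at Baseline - LDL-C at Day180) + LDL-C at Day180".
- **Step 2** classifies a participant whose LDL-C exceeds that threshold, and adds a second route: if "the subject's LDL-C value is greater than or equal to the LDL-C at Baseline, the subject is considered to have >80% of baseline". The visible text does not name the visit of the LDL-C value being compared.

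The SAP document history ties the appendix text to this endpoint: "Added responder definition as per the JAS 2017 guideline and 80% of the baseline value at Day 180".

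On reporting, SAP 2.7.2 says "For other secondary endpoints, only the descriptive statistics by treatment group will be presented" and "The two-sided 95% confidence interval for the proportion will be provided using the exact method of Clopper and Pearson". SAP section 4 declares one change from the protocol, the added JAS 2022 target, and nothing about this endpoint.

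**The concern.** The endpoint wording already fixes the rule: compare the Day 180 value with 0.80 times baseline. The appendix, offered as its derivation, takes 80% of the *reduction* from baseline to Day 180 and adds that back to the Day 180 value. That is a different quantity, and it moves with the participant's own Day 180 result.

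A programmer who follows the appendix on Day 180 values would count a subset of the participants that the endpoint describes. Each arm's proportion, and both limits of its Clopper-Pearson interval, could then only be equal to the correct value or too low. A table titled as the share above 80% of baseline would in fact show the share with no reduction at all.

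**Working it through.** **Inputs.** B = baseline LDL-C and D = Day 180 LDL-C. The endpoint (SAP 2.7.1) is D > 0.80B. The rule is steps 1 and 2 of SAP 5.5. The SD for illustration comes from SAP section 3, where the difference in mean percentage change is "expected to be >30% with a standard deviation of approximately 20" percent. The documents give no arm means at Day 180, so the means below are assumptions.

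**Threshold.** T = 0.8(B − D) + D = 0.8B + 0.2D. This equals 0.8B only if D = 0.

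| D as % of B | T as % of B |
|---|---|
| 90 | 98 |
| 80 | 96 |
| 70 | 94 |
| 50 | 90 |

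**Rule applied to the Day 180 value.** D > 0.8B + 0.2D ⇔ 0.8D > 0.8B ⇔ D > B. The second route in step 2 (D ≥ B) adds only equality, so the whole rule is D ≥ B.

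**Grid check.** Exact arithmetic was run on 91,476 pairs (B 70 to 300, D 5 to 400 mg/dL). The rule equals D ≥ B with 0 exceptions. It disagrees with D > 0.80B in 8,408 pairs, exactly those with D strictly between 80% and 100% of B. In every one of them the endpoint counts the participant and the rule does not.

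**Examples, B = 120 mg/dL (endpoint cut-off 0.80 × 120 = 96).**

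| D | % of B | T | Endpoint | Rule |
|---|---|---|---|---|
| 97 | 80.8 | 115.4 | yes | no |
| 100 | 83.3 | 116.0 | yes | no |
| 110 | 91.7 | 118.0 | yes | no |
| 119 | 99.2 | 119.8 | yes | no |
| 120 | 100 | 120.0 | yes | yes |

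**Possible size.** This applies only if step 2 uses the Day 180 value, and it assumes normal percentage change and complete data. The endpoint proportion is P(change > −20%) and the rule gives P(change ≥ 0%). For mean 0 and SD 20 these are Φ(20/20) = 84.1% and Φ(0) = 50.0%.

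| Assumed mean change | Endpoint, SD 20 (SD 15; SD 25) | Rule, SD 20 (SD 15; SD 25) |
|---|---|---|
| 0% | 84.1% (90.9; 78.8) | 50.0% (50.0; 50.0) |
| −30% | 30.9% (25.2; 34.5) | 6.7% (2.3; 11.5) |
| −50% | 6.7% (2.3; 11.5) | 0.6% (0.0; 2.3) |

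In participants at SD 20, with 95% Clopper-Pearson intervals:

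- Mean 0%, n = 54: 45 (70.7–92.1%) against 27 (36.1–63.9%).
- Mean −30%, n = 100: 31 (22.1–41.0%) against 7 (2.9–13.9%).
- Mean −50%, n = 100: 7 (2.9–13.9%) against 1 (0.0–5.4%).

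**Gap between arms.** At SD 20, the placebo-minus-active gap in points, endpoint versus rule, for assumed means (placebo, active) is:

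- (+10, −20): 43.3 versus 53.3
- (+5, −25): 49.3 versus 49.3
- (0, −30): 53.3 versus 43.3

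The gap can widen, stay the same or shrink, so no direction is claimed.

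**The case against.** The strongest reply is that the formula was written for something else. A redaction sits between the lead-in and step 1, just where the visit or analysis could be named, so the missing visit cannot be held against the plan. SAP 2.2 has a blacked-out class of efficacy objectives, and Protocol 6.4 and 8.3 show that LDL-C continues to be measured after Day 180.

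The structure of the rule also fits a later value X better. Exceeding D + 0.8(B − D) means having lost 80% of the Day 180 reduction. The second route in step 2 then does real work: if D > B, T = B + 0.2(D − B) lies above B, and that route catches X between B and T. On this reading the endpoint wording is complete without any formula, and the programs may have applied it directly.

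This reading is plausible, and it means the documents cannot show that a reported proportion is wrong. It also makes the figures for size conditional. It does not make the text right. With B = 120 and D = 30, 60 or 90, the threshold for a later value is 102, 108 or 114 mg/dL, that is 85%, 90% or 95% of baseline. That is neither 80% of baseline nor a Day 180 classification, yet the lead-in, the end of step 2, the cross-reference in 2.7.1 and the document history all present it as such.

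**Conclusion.** The concern holds: on neither reading does the visible rule derive the endpoint it is labelled with. On Day 180 values it is a cut-off at 100% of baseline; on a later value it is a recovery measure. That conclusion is algebra and needs no assumption.

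Whether the reported proportion is affected is less certain, because the visit is not visible and the documents do not show which rule was programmed. If steps 1 and 2 were run on Day 180 values, the understatement could be large: about 34 points at mean change 0% (84.1 − 50.0) and 24 points at −30% (30.9 − 6.7), under the assumptions stated with the calculation.

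The reach is limited to one descriptive secondary endpoint. The Dunnett-controlled primary test, the key secondary analyses and the power statement are untouched. It should be fixed, but it does not threaten the trial's main conclusion.

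**What to change.** In SAP Appendix 5.5, state for this endpoint: a participant is above 80% of baseline at Day 180 if Day 180 LDL-C > 0.80 × baseline LDL-C. If the existing two-step formula serves another analysis, move it under that analysis, name the visit whose LDL-C is compared with the threshold, and give the result its own label.

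Then check how any existing output for this endpoint was programmed, and rerun it if it used steps 1 and 2.

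The cost is one line of SAP text and a check of one derivation, with one descriptive table to rerun only if the check shows it is needed.
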